An important differentiating feature of bempedoic acid is that it does not inhibit cholesterol synthesis in skeletal muscle. In addition to preliminary data suggesting that only minor amounts of bempedoic acid enter skeletal muscle (<5% of systemic exposure), skeletal muscle does not express the enzyme required to activate bempedoic acid to ETC-1002-CoA and inhibit ACL. Therefore, bempedoic acid is not anticipated to mediate the adverse effects associated with inhibition of biological intermediates within the cholesterol biosynthesis pathway in skeletal muscle.

New Text:

An important differentiating feature of bempedoic acid is that, unlike statins, it does not inhibit cholesterol synthesis in skeletal muscle. ***The enzyme required to convert bempedoic acid to ETC-1002-CoA is not present in skeletal muscle.*** ~~In addition to preliminary data suggesting that only minor amounts of bempedoic acid enter skeletal muscle (<5% of systemic exposure), skeletal muscle does not express the enzyme required to activate bempedoic acid to ETC-1002-CoA and inhibit ACL.~~ Therefore, bempedoic acid is not anticipated to mediate the adverse effects associated with inhibition of biological intermediates within the cholesterol biosynthesis pathway in skeletal muscle; ***however, the safety of bempedoic acid and its metabolites regarding human skeletal muscle is not yet established.***

CHANGE 9 STUDY DESIGN REVISIONS

Location:

Section 2, Synopsis; Section 6.1, Overall Study Design

Original Text:

There will be no cap placed on randomization into any particular stratum. Approximately 750 eligible patients will be randomized 2:1 on Day 1 (Visit T1) to receive either bempedoic acid 180 mg (n = 500), or placebo (n = 250) once daily for 52 weeks. Randomized patients will return for clinic visits at Week 4 (Visit T2), Week 12 (Visit T4), Week 24 (Visit T5), and Week 52 (Visit T7). A phone visit will occur at Week 8 (Visit T3) and Week 36 (Visit T6).

New Text:

~~There will be no cap placed on randomization into any particular stratum.~~ Approximately 525 eligible patients will be randomized 2:1 on Day 1 (Visit T1) to receive either bempedoic acid 180 mg (n = ~~500~~**350**), or placebo (n = ~~250~~**175**) once daily for 52 weeks. Randomized patients will return for clinic visits at Week 4 (Visit T2), Week 12 (Visit T4), Week 24 (Visit T5), and Week 52 (Visit T7). A phone visit will occur at Week 8 (Visit T3) and Week 36 (Visit T6). ***For patients taking simvastatin 40 mg, there will be additional clinic visits to assess safety at Weeks 16 and 28 as well as telephone visits at Weeks 20 and 32.***

CHANGE 10 CONCOMITANT MEDICATIONS REVISIONS

Location:

Section 8.2.1, Lipid-Regulating Medications and Supplements

Original Text:

Statins

- Atorvastatin (Lipitor[®], Sortis[®])
- Fluvastatin (Lescol[®])
- Lovastatin (Mevacor[®], Altoprev[™])
- Pravastatin (Pravachol[®])
- Pitavastatin (Livalo[®], Lipostat[®])
- Rosuvastatin (Crestor[®])
- Simvastatin (Zocor[®])

New Text:

Statins

- Atorvastatin (Lipitor[®], Sortis[®])
- Fluvastatin (Lescol[®])
- Lovastatin (Mevacor[®], Altoprev[™])
- Pravastatin (Pravachol[®])
- Pitavastatin (Livalo[®], Lipostat[®])
- Rosuvastatin (Crestor[®])
- Simvastatin (Zocor[®]) (*doses \geq 40 mg are exclusionary*)

CHANGE 11 PROHIBITED MEDICATIONS REVISIONS

Location:

Section 8.2.2, Prohibited Medications

Original Text:

Patients will not have used medications (monotherapies or combination therapies) listed below within 4 weeks prior to screening or use these drugs during the study:

- New or planned dose changes of systemic corticosteroids. Stable doses of systemic corticosteroids at screening are allowed (\geq 4 weeks). Short-term intermittent use (<14 days) of pulse steroids are allowed. Topical steroids are allowed.
- Gemfibrozil (Lopid[®]) (as per co-administration instructions defined in the statin label)

- Cholestin (red yeast rice extract, also known as monascus purpureus extract) (2 weeks prior to screening)

New Text:

Patients will not have used medications (monotherapies or combination therapies) listed below within ***the allotted time period*** ~~4 weeks~~ prior to screening or use these drugs during the study:

- New or planned dose changes of systemic corticosteroids. Stable doses of systemic corticosteroids at screening are allowed (≥ 4 weeks). Short-term intermittent use (< 14 days) of pulse steroids are allowed. Topical steroids are allowed.
- Gemfibrozil (Lopid®) (as per co-administration instructions defined in the statin label) ***≥ 6 weeks prior to screening (Visit S1)***
- Cholestin (red yeast rice extract, also known as monascus purpureus extract) (≥ 2 weeks prior to screening)
- ***CETP inhibitors within the last 2 years prior to screening (Visit S1) except for evaceptrapib within the last 3 months prior to screening (Visit S1)***
- ***Mipomersen within 6 months prior to screening (Visit S1)***
- ***Lomitapide within 3 months prior to screening (Visit S1)***
- ***Apheresis within 3 months prior to screening (Visit S1)***
- ***Simvastatin > 40 mg***

CHANGE 12 ALLOWABLE MEDICATIONS REVISIONS

Location:

Section 8.2.3, Allowable Medications

Original Text:

Other concomitant medication must be stable prior to screening and, if possible, not be adjusted during the study except for reasons of safety.

The following must be stable for a minimum of 6 weeks prior to randomization:

- Postmenopausal hormone therapy
- Thyroid hormone supplements
- Fibrates (excluding gemfibrozil)

The following must be stable for a minimum of 4 weeks prior to screening:

- Hypertriglyceridemia therapy
- Lipid-lowering therapy, including dietary supplements and herbal remedies (except red yeast rice extract-containing products, which are exclusionary used for the purposes of lipid lowering).
- Diabetes medications

The following must be stable for a minimum of 3 months prior to screening and, if possible not be adjusted during the study except for reasons of safety:

- Antiobesity medications

New Text:

Other concomitant medications must be stable ~~prior to screening and~~, if possible, not be adjusted during the study except for reasons of safety.

The following must be stable for a minimum of 6 weeks prior to randomization:

- Postmenopausal hormone therapy
- Thyroid hormone supplements
- ~~Fibrates (excluding gemfibrozil)~~

The following must be stable for a minimum of 4 weeks prior to ~~screening~~**randomization**:

- ~~Hypertriglyceridemia therapy~~
- ~~Lipid lowering therapy, including dietary supplements and herbal remedies (except red yeast rice extract containing products, which are exclusionary used for the purposes of lipid lowering).~~
- Diabetes medications

~~The following must be stable for a minimum of 3 months prior to screening and, if possible not be adjusted during the study except for reasons of safety:~~

- Antiobesity medications

CHANGE 13 INVESTIGATIONAL MEDICINAL PRODUCT SUPPLY AND CONTROL REVISION

Location:

Section 9.1, Investigational Medicinal Product Supply and Control

Original Text:

A 35-day supply of single-blind placebo drug will be dispensed one time at Week -4 (Visit S2) for the 4-week placebo run-in period of the study. Double-blind IMP will be dispensed in 100 day supply increments to patients by appropriate clinical site personnel. Patients will receive one 100-day supply bottle at Week 0 (Visit T1), Week 12 (Visit T4), and two 100-day supply bottles at Week 24 (Visit T5).

New Text:

A 35-day supply of single-blind placebo drug will be dispensed one time at Week -4 (Visit S2) for the 4-week placebo run-in period of the study. Double-blind IMP will be dispensed in 100 day supply increments to patients by appropriate clinical site personnel. Patients will receive one 100-day supply bottle at Week 0 (Visit T1), Week 12 (Visit T4), and two 100-day supply bottles at Week 24 (Visit T5). *At Week 12, patients will return their first bottle and tablets will*

be counted by study personnel who will then dispense a second bottle. At Week 24, tablets from the second bottle will be counted and the final 2 bottles dispensed. At Week 52, tablets will be counted by study personnel from the 2 bottles dispensed at Week 24.

CHANGE 14 STUDY PROCEDURES REVISION

Location:

Section 10.1, Informed Consent

Original Text:

The patient must be adequately informed of the nature and risks of the study and understand the informed consent document (ICD). No study-related procedure will be performed until the patient has been completely informed of the study, has freely consented to take part in the study, and has signed and dated an ICD approved by the Sponsor (or designee) and the IRB or IEC. Participation in banking of samples for genetic analysis is optional for all patients, and consent for this must be documented in the patient's written informed consent.

New Text:

The patient must be adequately informed of the nature and risks of the study and understand the informed consent document (ICD). No study-related procedure will be performed until the patient has been completely informed of the study, has freely consented to take part in the study, and has signed and dated an ICD approved by the Sponsor (or designee) and the IRB or IEC. ~~Participation in banking of samples for genetic analysis is optional for all patients, and consent for this must be documented in the patient's written informed consent.~~

CHANGE 15 PROCEDURES AND SCHEDULE OF ASSESSMENTS REVISIONS

Location:

Section 10.2.1, Screening Week -5 (Visit S1; Day -35 ± 7 days)

Original Text:

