In addition, a summary of percent change from baseline to Week 12 LDL-C using the FAS, excluding patients who received additional lipid-lowering therapy by that time point (by Week 12 for the Week 12 time point), will be provided. Percent change from baseline to Weeks 24 and 52 on LDL-C will be analyzed similarly, with patients in the FAS who did not receive additional LDL or triglyceride-lowering therapy by that time point (by Week 24 for the Week 24 analysis by Week 52 for the Week 52 analysis) included in the analyses. Output from each time point will include the LSM and SE for each treatment group, as well as the placebo-corrected LSM, 95% CI, and p-value.

Additional post-randomization adjunctive lipid-modifying therapy

The number and percent of patients in each treatment group requiring additional (post-randomization) adjunctive lipid-modifying therapy will be summarized. Medications and the reasons for their additional treatment (hyperlipidemia vs. hypertriglyceridemia) will be summarized separately.

Safety Analyses

The summarization of AEs will include TEAEs, defined as AEs with an onset date on or after initiation of study treatment. TEAEs and SAEs will be summarized by system organ class (SOC), severity, and relationship to study drug for each treatment group. These AE summaries will include cumulative incidence (percent of patients experiencing the AE) and patient-year adjusted incidence rates. If appropriate, absolute and relative risk differences will be calculated using both cumulative incidence and incidence rates. Deaths, withdrawal from study treatment due to AEs, and withdrawal from the study due to AEs will each be summarized by treatment group.

Clinical safety laboratories, including hematology, blood chemistry, coagulation, HbA_{1c}, glucose, and urinalysis; PE findings; vital signs; ECG readings; and weight will be summarized by the value and by change from baseline in the value (where appropriate) at each postbaseline time point.

Hepatic Safety

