11.2. Adverse and Serious Adverse Events

11.2.1. Definition of Adverse Events

An AE is any untoward medical occurrence in a clinical investigation patient administered a pharmaceutical product, including control, and which does not necessarily have a causal relationship with treatment.

An AE can be:

- Any unfavorable and unintended sign (including an abnormal laboratory finding), symptom, or disease temporally associated with the use of a medicinal product, whether or not considered related to the medicinal product
- Any new disease or exacerbation of an existing disease
- Any deterioration in nonprotocol-required measurements of laboratory value or other clinical test (eg, ECG or x-ray) that results in symptoms, a change in treatment, or discontinuation from study drug
- TEAEs are defined as AEs that begin or worsen after the first dose of study drug
- Adverse drug reaction (ADR; see [Section 11.2.2](#))

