11.2.7. Treatment-Emergent Adverse Events

TEAE are defined as AEs that begin or worsen after the first dose of study drug.

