Percent change from baseline to Week 24 in LDL-C; change from baseline to Weeks 12, 24, and 52 in LDL-C; percent change from baseline to Weeks 12, 24, and 52 in HDL-C, non-HDL-C, TG, TC, apoB, and hs-CRP will each be analyzed using ANCOVA with treatment group, CV risk (ASCVD only; HeFH with or without ASCVD) and baseline statin intensity (high intensity, moderate intensity, low intensity) as factors and the relevant baseline as a covariate.

New Text:

In this hierarchical testing structure, each hypothesis is tested at a significance level of 0.05, two-sided. Statistical significance at each step is required in order to test the next hypothesis. If the primary endpoint meets the criteria for statistical significance, then the percent change from baseline to Week 24 in LDL-C will be tested; and so forth.

Percent change from baseline to Week 24 in LDL-C; *absolute* change from baseline to Weeks 12, 24, and 52 in LDL-C; percent change from baseline to Weeks 12, 24, and 52 in HDL-C, non-HDL-C, TG, TC, apoB, and hs-CRP will each be analyzed using ANCOVA with treatment group, CV risk (ASCVD only; HeFH with or without ASCVD) and baseline statin intensity (high intensity, moderate intensity, low intensity) as factors and the relevant baseline as a covariate.

Location:

Synopsis, Safety Analyses

Original Text:

No statistical analyses will be performed on any of the safety data in this study.

The summarization of AEs will include treatment-emergent AEs (TEAEs), defined as AEs with an onset date on or after initiation of study treatment. TEAEs and SAEs will be summarized by system organ class (SOC), severity, and relationship to study drug for each treatment group.

New Text:

~~No statistical analyses will be performed on any of the safety data in this study.~~

The summarization of AEs will include treatment-emergent AEs (TEAEs), defined as AEs with an onset date on or after initiation of study treatment. TEAEs and SAEs will be summarized by system organ class (SOC), severity, and relationship to study drug for each treatment group.

Location:

Synopsis, PK and Other biomarkers

Original Text:

PK plasma concentrations will be summarized at predose (T1) Weeks 24 and 52.

New Text:

PK plasma concentrations of *ETC-1002 and its metabolite ESP15228* will be summarized at ~~predose (T1)~~ Weeks 24 and 52.

CHANGE 8 MECHANISM OF ACTION REVISIONS

Location:

Section 4.2.1, Mechanism of Action

Original Text:

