18.1. ADVERSE EVENTS

Adverse Events (AEs) will be coded using MedDRA, Version 20.1.

Treatment emergent adverse events (TEAEs) are defined as AEs that started or worsened in severity after the first dose of double-blind study medication and prior to the last date of study medication + 30 days. AEs that occurred on day 1 will be only be determined as TEAE if the site indicated it occurred after first dose on the AE CRF.

See [Appendix 2](#) for handling of partial dates for AEs. In the case where it is not possible to define an AE as treatment emergent or not, the AE will be classified by the worst case scenario, i.e. treatment emergent.

An overall summary of number of patients within each of the categories described in the sub-section below, will be provided as specified in the templates. Listings will include TEAEs and Non-TEAEs.

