APPENDIX 2. PARTIAL DATE CONVENTIONS

Imputed dates will NOT be presented in the listings.

Algorithm for Treatment Emergence of Adverse Events:

START DATE	STOP DATE	ACTION
Known	Known	If start date < study med start date, then not TEAE If start date >= study med start date and <=study med end date + 30, then TEAE
	Partial	If start date < study med start date, then not TEAE If start date >= study med start date and <=study med end date + 30, then TEAE
	Missing	If start date < study med start date, then not TEAE If start date >= study med start date and <=study med end date + 30, then TEAE
Partial, but known components show that it cannot be on or after study med start date	Known	Not TEAE
	Partial	Not TEAE
	Missing	Not TEAE
Partial, could be on or after study med start date	Known	If stop date < study med start date, then not TEAE If stop date >= study med start date and <=study med end date + 30, then TEAE
	Partial	Impute stop date as latest possible date (i.e. last day of month if day unknown or 31st December if day and month are unknown), then: If stop date < study med start date, then not TEAE If stop date >= study med start date and <=study med end date + 30, then TEAE
	Missing	Assumed TEAE
Missing	Known	If stop date < study med start date, then not TEAE If stop date >= study med start date and <=study med end date + 30, then TEAE
	Partial	Impute stop date as latest possible date (i.e. last day of month if day unknown or 31st December if day and month are unknown), then: If stop date < study med start date and <=study med end date + 30, then not TEAE

Statistical Analysis Plan

START DATE	STOP DATE	ACTION
		If stop date >= study med start date and <=study med end date + 30, then TEAE
	Missing	Assumed TEAE

Algorithm for Prior / Concomitant Medications:

START DATE	STOP DATE	ACTION
Known	Known	If stop date < study med start date, assign as prior If stop date >= study med start date and start date <= end of treatment, assign as concomitant If stop date >= study med start date and start date > end of treatment, assign as post study
	Partial	Impute stop date as latest possible date (i.e. last day of month if day unknown or 31 st December if day and month are unknown), then: If stop date < study med start date, assign as prior If stop date >= study med start date and start date <= end of treatment, assign as concomitant If stop date >= study med start date and start date > end of treatment, assign as post treatment

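### SAP 18.1 counts adverse events that worsen after first dose as treatment-emergent, but the synopsis and the pre-dose-start rows of SAP Appendix 2 do not

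*Protocol*

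**What the plan says.** Treatment emergence is defined in several places in the current text.

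- **Protocol synopsis, Safety Analyses:** TEAEs are "defined as AEs with an onset date on or after initiation of study treatment". Only onset counts.
- **Protocol 11.2.1:** "TEAEs are defined as AEs that begin or worsen after the first dose of study drug". Section 11.2.7 repeats it: "TEAE are defined as AEs that begin or worsen after the first dose of study drug".
- **SAP 18.1:** "AEs that started or worsened in severity after the first dose of double-blind study medication", with a window that closes 30 days after the last dose. It points to Appendix 2 "for handling of partial dates for AEs" and adds that an event which cannot be classified is taken as treatment-emergent.
- **SAP Appendix 2:** the appendix is titled for partial dates, but its adverse event table is headed as the algorithm for treatment emergence and begins with rows for fully known dates. For a known start, whatever the state of the stop date, the rule is: "If start date < study med start date, then not TEAE". A partial start that cannot fall on or after first dose gets the same result. For a missing start, or a partial start that could fall on or after first dose, the table turns to the stop date: "If stop date >= study med start date and <=study med end date + 30, then TEAE". If the stop date is missing as well, the event is assumed to be a TEAE.

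Protocol 12.1 gives the SAP precedence over the protocol for data analysis. Protocol 11.2.3 collects adverse events from informed consent onward and lists onset, resolution, severity and seriousness among the recorded items. It lists no date of worsening.

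**The concern.** Adverse events are recorded through roughly five weeks of screening and placebo run-in before Day 1 (Protocol 6.3 and 11.2.3), so some patients will enter double-blind treatment with an event already open. Randomization balances those open events between the arms on average. If the drug then makes them worse, the worsening is a between-arm difference that the safety tables ought to show. SAP 18.1 says it should be counted. The pre-dose-start rows of Appendix 2 say it should not.

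At stake are the TEAE summaries by severity and relationship, the serious and discontinuation summaries, and the summary of adverse events of special interest (AESIs), in SAP 18.1.1 to 18.1.6. The corresponding monitoring committee tables in SAP Appendix 3 (14.3.1.1 to 14.3.1.6 and 14.3.1.8) are also affected. SAP 18.1.6 does not itself say treatment-emergent, but committee table 14.3.1.8 is of treatment-emergent AESIs. Muscle complaints are the natural example. They are among the most frequently reported events to date, muscular events are of special interest (Protocol 11.4), and Protocol 4.2.1 says skeletal muscle safety has not been established.

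**Working it through.** The documents give no figure to reproduce here, so the check is to apply each rule to the same event. Take a hypothetical event that starts on Day -10, worsens on Day 40 and stops on Day 60, in a patient whose first double-blind dose is on Day 1 and who is still on drug at Day 60.

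| How the event is recorded | Synopsis | Protocol 11.2.1, 11.2.7 | SAP 18.1 | SAP Appendix 2 |
|---|---|---|---|---|
| A. One record, known start Day -10 | not TEAE | TEAE | TEAE | **not TEAE** |
| B. New record at worsening, start Day 40 | TEAE | TEAE | TEAE | TEAE |
| C. Partial start that could be on or after first dose; stop Day 60 or missing | cannot be applied to the date as recorded | TEAE | TEAE | TEAE |
| D. Missing start; stop Day 60 or missing | cannot be applied | TEAE | TEAE | TEAE |
| E. Partial start that must precede first dose | not TEAE | TEAE | TEAE | **not TEAE** |

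Three things follow.

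1. Appendix 2 contradicts SAP 18.1 in cases A and E only. In case B the new record has a post-dose start. In cases C and D the stop date, or the default for a missing stop date, brings the event in.
2. The worst-case default in SAP 18.1 does not rescue case A. It applies where emergence cannot be determined, and a complete pre-dose start date lets Appendix 2 determine it, as not treatment-emergent.
3. The ordering is odd. An event with no start date that stops on treatment is counted, while a fully dated run-in event that becomes severe on drug is not.

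Appendix 2 and SAP 18.1 also differ on Day 1. SAP 18.1 counts a Day 1 event only if the site marked it as occurring after the first dose, whereas Appendix 2 counts any start on or after the first-dose date. This is a separate, smaller mismatch, but it shows that the table was not reconciled with the definition.

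**The case against.** The best reply is that SAP 18.1 is the operative definition. The SAP supersedes the protocol, so the synopsis sentence does not drive any table. SAP 18.1 expressly includes worsening and cites Appendix 2 for partial dates only, so a row for complete dates in a partial-date appendix need not override it. Protocol 11.2.3 also says that a condition present at screening or baseline which changes in severity or seriousness should be reported as an adverse event, and 11.2.1 treats the exacerbation of an existing disease as an adverse event. If sites enter the worsening as its own event with its own date, case B applies and nothing is lost.

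Much of this stands. The synopsis wording is a matter of alignment. A reader might infer that 11.2.3 shuts out worsened run-in events, and the text does not support that. It leaves open whether an already recorded run-in event gets a new record and what onset date that record carries. The eCRF and its completion guideline might settle this, but they are not among the documents.

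The reply does not remove the conflict within the SAP. Appendix 2 holds the only stepwise rule for setting the TEAE flag, its heading covers treatment emergence in general, and its first row is for known dates. A programmer could reasonably code from it. Without a specified date of worsening, the worsening limb of SAP 18.1 has no stated data source.

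**Conclusion.** The contradiction is real and sits in current text. As written, the Appendix 2 rows for a known start, or for a partial start that must precede first dose, misclassify a worsened run-in event under the SAP's own definition. The loss from the tables rests on two conditions that the documents do not settle: that Appendix 2 is programmed as written, and that the event keeps its run-in onset date.

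Stronger readings are tempting but not supported:

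- **That Appendix 2 works by start date alone.** It uses the stop date, or assumes emergence, for missing starts and some partial starts.
- **That worsened run-in events necessarily drop out of every TEAE table.** This holds only under the two conditions above.
- **That worsening would be visible only in listings.** Withdrawals from treatment (SAP 9), adjudicated clinical endpoints (SAP 18.3) and laboratory abnormalities including CK (SAP 18.4) are tabulated without a stated TEAE filter.
- **That the number of patients can be estimated.** The documents give no rate of run-in events, of their persistence to Day 1, or of worsening. Assumed rates of 20% to 40%, 30% to 50% and 2% to 10% give 750 x 0.20 x 0.30 x 0.02 = 0.9 at one end and 750 x 0.40 x 0.50 x 0.10 = 15 at the other. That spread only reflects the assumptions. It also ignores that patients with a study-drug-related run-in event are not randomized (Protocol 8.3).
- **That the lost events are the severe ones.** A change from mild to moderate is also worsening.

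The number affected is probably small. The point should still be corrected, because the algorithm states a rule that its own definition rejects, and the repair is cheap.

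**What to change.** 1. In SAP Appendix 2, add a branch to the rows for a known pre-dose start and for a partial start that must precede first dose: if severity increases after the first double-blind dose and up to last dose + 30 days, the event is a TEAE.
2. Reword the synopsis sentence under Safety Analyses to match Protocol 11.2.7.
3. In Protocol 11.2.3 or the eCRF completion guideline, state that worsening of an ongoing run-in event is entered as a new record, with the date of worsening as its onset. This gives the SAP 18.1 definition a date that can be programmed.

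The cost is one algorithm branch, one sentence and one completion instruction. TEAE counts may rise slightly. Where the new record and the run-in record fall under the same preferred term, SAP 18.1.2 and 18.1.3 already reduce repeats within a patient to the worst case, so the severity and relationship summaries should not count that patient twice.
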